This is a repeated measures study that is a pilot randomized controlled trail, four parallel groups, and double-blind design. It is used to examine the effects of Paro intervention on cognition, executive functions, and mental well-being for specific attachment older adults with dementia at before, during and after the intervention. A mixed between-within subjects analysis of variance design will be used to assess the immediate effects of the 6-week Paro intervention on cognitive, executive and three mental well-being related variables for different attachment orientations of older adults living LTC facilities. Outcomes of interest measures will include dopaminergic activities variations by FTT and HRV changes at three time points: before the intervention (T0), middle of intervention (week-3, T1), the end of intervention (week-6, T2), and 1 month after the intervention (T2). Furthermore, the change of oxytocin level will be assessed at baseline and the end of the intervention.

The purpose of this study is to examine the effect of Paro intervention on neurobiologically changes for older adults with dementia in LTC. The research design is shown in Table1.

Table 1 Research design for Paro intervention

Group	Subgroup	T0	Intervention	T1	T2	T3
Security	Experiment	O ₁	X	O ₂	O ₃	O ₄
	Control	O ₁		O ₂	O ₃	O ₄

Experiment group: Paro intervention; Control group; O₁: Baseline; O₂: Week 3; O₃: Week 6; O₄: Week 10

4. Sample size, Sampling, Settings, and Participants Recruitment

There are 120 participants will be recruited into this pilot randomized controlled trial from LTC facilities in southern Taiwan. Older adults will be randomly assigned to four groups: experimental group or control group. The purpose of sampling will be used to allocate 60 participants either to the experimental group or the control group using computer generated sampling. Contact has been made with the Directors of the LTC facilities who have expressed their interest in being involved in the study. Directors will invite older adults who meet the inclusion criteria to participate in this study.

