The inclusion criteria of elderly participants will be: (1) aged 65 years or over; (2) Mild to moderate dementia (3) an ability to communicate in Mandarin or Taiwanese; and (4) has been living in the LTC facility at least 3 months. Older adults who: (1) have severe difficulty in communication; (2) are totally dependent on carers for daily activity; (3) have a diagnosed infectious disease, severe dementia, and severe mental illness such as schizophrenia and delusional disorder, will be excluded from the study.

5. Intervention

Participants in the experimental group will receive a group (6-8 people as a group) , facilitated, and 30-minute weekly session Paro intervention for 6 weeks. The control group will receive care as usual activities, such as painting, drawing, and craft, which are provided by each facility.

6. Paro

Paro (Personal Assistive Robot), was developed by [name] in Japan. It has the appearance of a baby harp seal; the current version (V9) weighs 2.5 kilograms and is approximately the size of a new-born baby. Paro is equipped with an array of tactile sensors that monitor sound, light, temperature and touch via artificial intelligence software. Paro can show human-like emotional reactions when it feels surprised, happy, or angry, and it will cry when it is neglected or not receiving sufficient attention.

In this study, Paro will be used as a Robot-pet companionship intervention with the aim to improve mental health in terms of different attachment orientations. Robot-pet companionship interventions are based on human-animal interactions aimed at providing physiological, psychological, and social benefits (Robinson et al., 2015; Chang et al., 2013; Cohen-Mansfield et al., 2010; Shibata et al., 2004).

Figure 1. The images of Paro

7. Procedure of interaction records

Participants in experimental groups will receive a group, facilitated, 30-minute weekly session of Paro intervention. A trained research assistant (RA) give the Paro to the participants at the start of each session, repeating the same introductory script each time. The RA facilitate the participant interact with the Paro during the intervention, after 30 minutes RA will use the same ending script to end the session and goodbye to participants.

8. Outcome measures

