Participants in the experimental group will receive a group (6-8 people as a group), facilitated, and 30-minute weekly session Paro intervention for 6 weeks. The control group will receive care as usual activities, such as painting, drawing, and craft, which are provided by each facility.

6. Procedure of interaction records

Participants in experimental groups will receive a group, facilitated, 30-minute weekly session of Paro intervention. A trained research assistant (RA) will give the Paro to the participants at the start of each session, repeating the same introductory script each time. The RA facilitate the participant interact with the Paro during the intervention, after 30 minutes RA will use the same ending script to end the session and goodbye to participants.

7. Outcome measures

The process and outcome of measurement will be blinded and assessed by another RA at four time points: baseline (T0), Week 3(T1), Week 6 (T2), and 1 month after the end of intervention(T3). The primary outcomes are global cognitive function and executive functions. The Mini-Mental State Examination (MMSE) will be used to assess participants' global cognitive function. The executive functions include two components such as working memory (WM) and response inhibition, which will use computerized tasks to assess the changes of executive functions for order adults before and after intervention. Working memory will be assessed using verbal WM and visuo-spatial WM tasks. Response inhibition will be assessed employing color word stroop

(CWS), stop signal (SS), and go/no-go (GNO) tasks. The secondary outcome measures are loneliness (UCLA version-3), Depression (GDS-SF), and Mental well-being (WEMWBS).

Table 2 Measurement time points and measurements

Instrument	Week-0 (T0)	Week-3 (T1)	Week-6 (T2)	Follow- up (T3)
Demographics/disease information	√			
RAAS-C	√			
Outcome measure				
-MMSE	√	√	√	√
-Executive Functions	√	√	√	√
-Loneliness (UCLA)	√	√	√	√
-Depression(GDS-SF)	√	√	√	√
-Mental well-being (WEMWBS)	√	√	√	√

Note. √, collect data; MMSE; executive function; UCLA, the University of California Los Angeles Loneliness Scale version 3; GDS-SF, Geriatric Depression Scale - Short Form; WEMWBS, Warwick-Edinburgh Mental Well-being Scale.

(1) Demographic data

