To probing the change of the markers, a series of paired sample t-test will be used for each group. To testing the research hypothesis, a mixed designed generalized linear model (GLM) will be employed to test the effects of arms on the differences between the pre and post-test in relation to outcome measures, including oxytocin level, dopamine and HRV changes for different attachment orientations of older adults living LTC facilities. In order to increase precision in estimating the effect of interest, the possible confounding effects of the covariates, such as age, education, etc, will be used to take into account as covariate in the model. The effect size will be calculate to show the magnitude and direction of the effect in the attachment-specific group relative to the control for each outcome variable. In order to identify the optimal duration of clinical application for this intervention, a trend analysis will be conducted. Exploratory additional analysis will be conducted to test the interaction between intervention, and potential biomarker on clinical evaluation. A p value $< .05$ will be taken as the level of statistical significance. The 95% confidence interval around the differences will be calculated.

II. Expectation Outcome

We expect to identify positive effect of Paro intervention on cognitive, executive functions, depression, loneliness, and mental well-being for older adults with dementia.

III. Ethical Considerations

Ethics approval for both phases of the study will be sought from Cheng-Kung University Human Research Ethics Committee and prior to the commencement of the study. Ethics approval for the study will also be sought from the participating LTC facilities in Taiwan prior to the commencement of the study. The researcher will inform the participants about the aims and objectives of the research study and what their participation will involve. Participants will be assured that (a) their participation will be on a voluntary basis and they are under no obligation to participate; and (b) they are free to withdraw from the study at any time without explanation, penalty or compromising their relationship with the LTC. A signed consent form will be sought from each participant. There are no foreseeable risks associated with participation in the intervention for participants.

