All collected data will be stored electronically with password-protection to prevent unauthorised access to the data. All data and related documents will be kept in a key-locked cabinet for 5 years before being destroyed. Although demographic data will be requested, participants will remain anonymous. For quantitative data, all data will be de-identified at data entry and results will be reported in general terms. For qualitative data, the digital interview files will be deleted after transcription. Data will be de-identified with codes and content separated. Anonymity will be maintained via pseudonyms for direct interview quotes used in the reporting of findings.

For ethical consideration, our research team will provide opportunity for the elderly in the control group who receiving plush toy. They can choose to partake two 50-minute sessions of group-based Paro interventions to experience interactions with Paro after completing their intervention and follow up.

IV. Expected difficulties encountered and solutions

1. Difficulties for participant's recruitment and active engagement data collection

This study will conduct 6 weekly sessions of Paro intervention in LTC facilities. Older adults may feel anxious about interaction with a Paro or withdraw from the

intervention. For dealing with this potential problem, the possible solutions are as below:

- (1) The research team will hold a briefing to explain the research process to the participating institutions in order to attract the participation of the heads of the institutions.
- (2) Introducing the Paro to family and encourage family and workers interacting with the Paro. Also, encouraging participants share their experiences with his/her friends.
- (3) Provide incentives or motives for participants and explaining the research procedure and potential benefits for them. The research team will show a Paro video or demonstrate Paro interaction to participants and facilities to introduce how the Paro interact with other older adults and share with experiences to using it.

2. Difficulties in quality assurance and quality control in Paro research

As a limited number of Paro, each round will plan to recruit 6 participants. The research team will extend the study periods to recruit enough participants. For controlling the research quality, the possible solutions are as below:

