- (1) *To increase the quality and consistency of interaction with Paro.* Each facility will recruit two volunteering care staff to participate in the study. Staff will receive 1 hour of Paro interactive training. Each care staff will provide incentives and motives to increase motivation to partake this study.
- (2) *For reducing the interference or contamination among the four groups.* This study will recruit control group and experimental groups in different levels to prevent interference among groups receiving intervention at the same time in the same facility.
- (3) *To reduce the human interferences.* In order to establish a research consensus among institutional staff, we will provide a 60-minute course to workers in participating facilities, the purpose of which is to help them to familiarize with our programs and procedures

1. Work Projects

- (1) Contact with the long-term care facilities and design a flyer for recruitment of research participants.

- (2) Research assistants training, establishing standardized procedures of intervention, developing data collection steps, related knowledge of processes in Paro intervention.
- (3) For research fidelity, monitoring experimental group and control group by weekly check, holding regular steering meetings to maintain the quality and consistency of program implementation.
- (4) Conduct data collection using questionnaires.
- (5) To submit the manuscript to international conferences and health-related journals.
- (6) To submit the final report for the project.

2. Expected the contribution of the Research

This study will thoroughly examine the effect of Paro intervention on cognitive, executive functions, mental well-being for specific attachment orientation older adults with dementia. This is the first study we know of to utilize a rigorous research design to examine the effect of intervention and explore the relationship between different attachment orientation older people and Paro. The findings of this study will provide strong evidence and advance knowledge of the mechanism of Paro intervention in LTC of Taiwan and be able to link this result to international studies. The findings of the research will publish in international journals.

3. Expected Contribution of Research to Personnel

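### Paro is given in about 8–10 groups of 6–8, but the arm tests in Studies 1 and 3 treat participants as independent; correlation specific to those groups, or to the levels separating the arms, would make p-values and intervals too optimistic

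*Combined protocol and SAP*

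**What the plan says.** **Delivery.** Study 3, I.5 (Intervention) states: "Participants in the experimental group will receive a group (6-8 people as a group), facilitated, and 30-minute weekly session Paro intervention for 6 weeks". Study 1, II.5 gives the same group size. Controls have the usual activities of their facility, and no therapy-group structure is described for them. The quality-control section (Study 3, IV.2; the same text is in Study 1, V.2) adds: "As a limited number of Paro, each round will plan to recruit 6 participants". It does not say whether the six are from one arm or both. The measure planned against contamination is to "recruit control group and experimental groups in different levels to prevent interference among groups receiving intervention at the same time in the same facility".

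**Analysis.** Study 1, II.3 and Study 3, I.3 both say: "A mixed between-within subjects analysis of variance design will be used to assess the immediate effects of the 6-week Paro intervention". They name the time points and attachment orientation, and no cluster term. Study 3, I.8 (Data analysis) also covers the Study 1 biomarkers, because Study 1 has no analysis section. There "a mixed designed generalized linear model (GLM) will be employed to test the effects of arms on the differences between the pre and post-test", and "the possible confounding effects of the covariates, such as age, education, etc, will be used to take into account as covariate in the model". For change within an arm, "a series of paired sample t-test will be used for each group". The section sets significance at p < .05 and promises 95% confidence intervals.

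No therapy-group, facility or level term, random effect for clusters, robust standard error or ICC appears in any of these sections.

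**The concern.** People who share six facilitated sessions also share a facilitator, companions and a group atmosphere. If these affect change, outcomes within a group are correlated, and 60 people in 8 to 10 groups carry less information than 60 independent people. An analysis that ignores this understates the standard error of the Paro-arm mean. The p-values are then too small and the intervals too narrow.

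The project's own aims make this plausible. Study 1, II.2 objective (5) relates group process to the neurobiological measures, and Study 2, II.2 objective (4) relates it to change in loneliness and depression. A plan that expects group process to matter should not assume that group membership does not.

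The separation of the arms by level within a facility is a second possible source: anything particular to a level is then shared within an arm and differs between arms.

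**Working it through.** **Inputs from the documents.** 120 participants, 60 per arm; Paro groups of 6–8; significance level 0.05. Sidedness is not stated, and two-sided is assumed from the 95% interval. The plan's own figure checks only as 60 + 60 = 120. No effect size, standard deviation, power or ICC is given, so it cannot be reproduced further.

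**Assumed.** The ICC of change within a Paro group is set at 0.01, 0.02, 0.05 and 0.10, with equal total variance in the two arms.

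**Number of groups.** 60/8 = 7.5 to 60/6 = 10, so about 8 to 10.

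**Step 1: clustering in the Paro arm only.** With m members per group:

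- Paro-arm design effect: DEFF = 1 + (m − 1) × ICC
- true over reported SE of the arm difference: R = √((1 + DEFF)/2)
- true two-sided error of the arm test: 2Φ(−1.96/R)
- true two-sided error of a paired t-test in the Paro arm: 2Φ(−1.96/√DEFF)

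| ICC | DEFF (m = 6, 8) | R | Arm test | Paro paired t-test |
|---|---|---|---|---|
| 0.01 | 1.05, 1.07 | 1.012, 1.017 | 5.3%, 5.4% | 5.6%, 5.8% |
| 0.02 | 1.10, 1.14 | 1.025, 1.034 | 5.6%, 5.8% | 6.2%, 6.6% |
| 0.05 | 1.25, 1.35 | 1.061, 1.084 | 6.5%, 7.1% | 8.0%, 9.2% |
| 0.10 | 1.50, 1.70 | 1.118, 1.162 | 8.0%, 9.2% | 11.0%, 13.3% |

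Example: m = 8 and ICC 0.05 give DEFF = 1 + 7 × 0.05 = 1.35, R = √(2.35/2) = 1.084 and 2Φ(−1.96/1.084) = 7.1%. Simulated t-tests on change (40,000 trials per cell) agree: 6.5% and 7.8% for ten groups of 6, and 6.9% and 9.2% for eight groups of 7–8, at ICC 0.05 and 0.10.

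**Step 2: a facility effect shared by both arms.** With ten facilities each holding 6 + 6 participants and no group effect, the unadjusted test is conservative: 4.6% at facility ICC 0.05 and 4.0% at 0.10. With both sources present (100,000 trials per cell):

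| Group ICC | Facility ICC 0.05 | Facility ICC 0.10 |
|---|---|---|
| 0.02 | 5.0–5.4% | 4.5–5.0% |
| 0.05 | 5.9–6.6% | 5.5–6.1% |
| 0.10 | 7.5–8.5% | 6.9–8.1% |

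**Step 3: separate level effects of equal size in both arms, no shared facility effect.** Simulated error of the arm test is 6.1–6.5%, 7.8–8.9% and 11.0–13.0% at ICC 0.02, 0.05 and 0.10.

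**Step 4: does a group term repair it?** Simulation (13,000 trials per cell) used one post-baseline value, baseline, fixed facility effects (facility ICC 0.05), a therapy-group random effect in the Paro arm only and Satterthwaite degrees of freedom. Fits with a zero group variance were kept.

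| Group ICC | With group term | Without group term |
|---|---|---|
| 0 | 3.4–3.8% | 4.6–5.0% |
| 0.02 | 3.6–4.2% | 5.6–5.7% |
| 0.05 | 4.2–4.5% | 6.8–7.1% |
| 0.10 | 4.1–4.9% | 8.2–9.5% |

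Baseline and facility alone do not remove the inflation; the group term does, at the price of some conservatism. It does not fully cover level effects. With five facilities and two Paro groups sharing each Paro level, a model of this kind fitted to change scores still gave 8.1% and 11.2% at level ICC 0.05 and 0.10 (6,000 runs). With one Paro group per facility there was no inflation.

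**The case against.** The strongest reply is that nothing in the documents shows clustering of any size, and several features limit it: identical opening and closing scripts, six half-hour sessions, a separate blinded assessor, individual testing in a quiet room, and Study 1 primary outcomes that are an assay, tapping counts and heart rate variability. At ICC 0.01–0.02 the arm test is at 5.3–5.8%, and at 0.02 the repaired test (3.6–4.2%) is no nearer 5% than the unrepaired one (5.6–5.7%). Both studies are also called pilots.

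This stands as a limit on size. It does not supply protection: the scripts cover the start and end of a session, not the interaction between, and blinded assessment does not remove a shared experience. The project also says that it expects strong evidence and a care model for long-term facilities, which is more than a pilot claims.

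Two further defences fail. The word mixed in the GLM describes a between-within design, not a cluster random effect. The open end of the covariate list extends a list of personal confounders such as age and education, and specifies no group term.

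A reader might infer that any correlation within Paro groups, or the missing facility term by itself, makes the results optimistic. That does not follow. A facility effect common to both arms also makes group members alike, yet ignoring it makes the arm test conservative (step 2).

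A reader might also infer that Study 2 copies one climate score to all members of a group and analyses 60 values. No section plans this. What Study 2 means by groups, and its unit for scoring climate, are undefined. That is a separate request for clarification and not part of this point.

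**Conclusion.** The point holds in a conditional form. The arm analyses and paired t-tests of Studies 1 and 3 treat as independent 60 people who are treated in about 8 to 10 groups. If change correlates within Paro groups, or within the levels that separate the arms, beyond a facility effect shared by both arms, the tests exceed 5% and the intervals cover less than 95%.

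The size rests wholly on assumed ICCs and is illustrative, not a bound. It is minor at 0.01–0.02 and material from about 0.05, and larger for the paired t-tests than for the arm comparison. Shared facility effects would reduce it and separate level effects would increase it. The documents do not show which of these applies, so they do not support saying that the planned tests are in fact inflated, only that the plan has no protection if they are. This should be fixed before analysis, because group membership is easy to record during the study and may not be recoverable afterwards.

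**What to change.** 1. **Record** therapy-group ID, facility and level for every participant.
2. **Prespecify one arm analysis per outcome.** Keep the planned covariates, add the baseline value and facility, and include a therapy-group random effect in the Paro arm only, with Satterthwaite degrees of freedom. State that the model is kept if the group variance is estimated as zero.
3. **Match the model to the visits.** Use time and arm-by-time terms only for outcomes with more than one post-baseline visit. Oxytocin is measured only at baseline and week 6 (Study 1, Table 2), so it has a single post-baseline value and no time terms.
4. **Base conclusions on the between-arm estimate.** Treat the within-arm paired t-tests as descriptive, or give them standard errors that allow for therapy group.
5. **State the limit on levels.** If several Paro groups share a level, say that level effects cannot be fully separated from arm and that the group term does not fully protect against them.

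**Cost.** Three data fields and some analysis wording. Standard errors of the arm effect are about 1–8% wider at ICC 0.01–0.05 and 12–16% at 0.10. With 8 to 10 groups the group variance is imprecise and often estimated as zero, in 50–51% of simulated trials at ICC 0.02. The test is then somewhat conservative and loses some power when there is little or no clustering. The simulation covered a single post-baseline value, so the repeated-measures version should be checked in the same way before it is fixed in the plan.

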Participants' demographics such as age, gender, education level, religion, number of children, and previous pet ownership will be collected. Disease-related information will include the length of stay in the LTC, type of depressive disorder, any other chronic disease, a medication audit including antidepressants and other medications, and Barthel index of Activities of Daily Living.

(2) The Chinese version of Mini-Mental State Examination (MMSE)

The Mini-Mental State Examination (Folstein, Folstein, & McHugh, 1975) is a widely used tool that screens for levels of cognitive impairment, using the concepts of orientation, registration, attention and calculation, recall, and language. The MMSE has been translated into Chinese with small modifications based on the sociocultural differences of the Chinese population, and has been utilised as a dementia screening instrument for epidemiological studies (Zhang et al., 1990). The MMSE has good internal consistency with a Cronbach alpha of .91 (Marioni, Chatfield, Brayne, & Matthews, 2011). In a previous study, the MMSE has shown good sensitivity of 78.4% and a specificity of 87.8 % in primary care (Mitchell, 2008). The Cronbach alpha was .83 to .84 in older Taiwanese populations (Chung, Chiou, & Chou, 2009; Lou, Dai,

Huang, & Yu, 2007). The MMSE score ranges from 0 to 30. In general, a cut-off point higher than 24 indicates normal cognition; 20–23 mild cognitive impairment; 10–19 moderate cognitive impairment; and 0–9 severe cognitive impairment. In this study, the cut-off point was based on a study by Zhang et al. (1990) in which the level of cognitive impairment varies according to educational level: 17/18 for older people without formal education, 20/21 for those with 1–6 years of education (primary school), and 24/25 for participants with more than six years of education (middle school or higher) in Chinese older adults.

(3) Core components of executive functions- WM and response inhibition

The two core executive functions, WM and inhibition, were assessed using computerized tasks. Working memory was assessed using verbal WM and visuo-spatial WM tasks. Response inhibition was assessed using CWS, SS and GNG tasks. All older adults with dementia will be individually tested in a quiet room. The order of task administration is the same for all participants and they will receive a practice session prior to all the tasks. A period of rest is given between two tasks.

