Color word Stroop task (Stroop, 1935; Macleod, 1991): In this task different colour words will appear on the computer screen one at a time. The task is to name the color the word is printed, disregarding what the color word reads. The colour of the word printed is in the same color as the meaning of the word (congruent trials, eg; “red” is printed in red colour), or it is different from the meaning (incongruent trials, eg; word “green” is printed in blue colour). There are 75 congruent trials and 25 incongruent trials for one test session. Incorrect responses on incongruent trials are taken to assess the level of inhibitory control. The higher the errors the lower the interference control is.

Visuo-spatial WM task: A 4×4 matrix with 16 squares is displayed on the computer screen as a pig house with a pig appearing in each window one at a time. The task is to recall in reverse order the locations where each target (pig) has appeared. The test start with a span length of two, that is, two pigs appear one after another. Each span consist of two trials and the test is concluded when the participant failed both trials at that same span length. Each correct location is given one point with a maximum score of 88. The score is taken as the measure of Visuo-spatial WM. At the end of the test, obtain score is automatically displayed on the computer screen.

Stop signal task: It assess the ability to inhibit ongoing responses. This is like a

car game (Tillman, Thorell, Brocki & Bohlin, 2007) where a car appears on the computer screen. Every time the car appear, the participant is supposed to press a designated key as fast as possible to drive the car away. But when a stop-sign board appeared next to the car, participants has to refrain from pressing for the car to stand still. Each session in this task consist of 24 trials with six stop-signs-trials. Number of incorrect presses in stop sign (commission errors) is considered as the measure of inhibition and it is automatically displayed on the screen at the end of the task.

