Verbal WM task (adapted from Towse, Hitch & Hutton, 1998): These are power point slides. Each slide has different numbers of red circles with squares as distracters. The task is to count the total number of red circles in each slide, keep total in memory and recall the numbers in the correct order. The test start with a length of memory recall (span) of two, that is, the participant had to recall two slides first. Each level of memory recall consist of three trials and the test is concluded when the participant failed two trials out of three at that same length of recall. If the participant is successful in 2 out of three trials, he/ she is allowed to go to the next span. A total score is calculated after adding a mark for each correct recall (Towse, Hitch & Hutton, 1998).

Go/no-go task (two versions: colour and shape): It assess ability to inhibit pre potent responses. The subject is presented with four different stimuli on the screen, one at a time in random order. There are two squares and two circles in blue and red. In the first session, the subject is instructed to respond by pressing a key each time when a blue figure appeared (go-trials) regardless of the shape, and not to respond when a red figure appear. In the second session, the subject is instructed to respond each time when a square appear, regardless of the color, and not to respond when a circle appear (Berlin & Bohlin, 2002). Together the two consecutive sessions include 60 stimuli with 77% go-trials. The number of incorrect responses (commission errors) is used as a measure of inhibition and it is automatically displayed on the screen at the end of the task.

(4) The UCLA Loneliness Scale version 3

The UCLA Loneliness Scale Version 3, a 20-item scale, was developed by Russell (1996). It is used to measure a person's subjective feelings of loneliness and feelings of isolation. Each item on the scale is rated from 1 (Never) to 4 (Often) with a total score ranging from 20 to 80. The scale does not identify a cut-off score that defines loneliness. The higher the score, the more severe a person's feelings of loneliness. This scale has good reliability with Cronbach's alpha of internal consistency ranging from 0.89 to 0.94

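### Stop-signal and go/no-go inhibition are scored on commission errors alone, so a participant who never responds gets the best possible score on part of Study 3's primary outcome

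*Combined protocol and SAP*

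**What the plan says.** Study 3, section 7 (Outcome measures) states: "The primary outcomes are global cognitive function and executive functions". Under item (3) of that section, "Response inhibition was assessed using CWS, SS and GNG tasks". The scoring rules are:

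- **Stop-signal task.** "Each session in this task consist of 24 trials with six stop-signs-trials". The score: "Number of incorrect presses in stop sign (commission errors) is considered as the measure of inhibition".
- **Go/no-go task.** "Together the two consecutive sessions include 60 stimuli with 77% go-trials". The score: "The number of incorrect responses (commission errors) is used as a measure of inhibition".
- **Colour word Stroop.** There are 75 congruent and 25 incongruent trials. "Incorrect responses on incongruent trials are taken to assess the level of inhibitory control", and more errors mean poorer control.

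The plan does not use go-trial hits, omissions or go reaction time, and it does not use the congruent Stroop trials. It sets no minimum go accuracy and no rule for an uninterpretable session. The testing safeguards are a quiet room, a practice session without a stated pass mark, and rest between tasks. Section 8 (Data analysis) handles missing data by carrying the last observation forward.

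**The concern.** A commission count measures inhibition only if the participant is responding. Someone who has lost the instruction, is slow or has stopped pressing makes few false presses for a reason unrelated to inhibition, and the score credits this as good control. The trial enrols people with mild to moderate dementia, in whom patchy responding is plausible.

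What is at stake is a between-arm comparison on a primary outcome. Responding is measured after randomisation and can change during the study. If it differed between arms at week 3, week 6 or follow-up, the scores would differ even with inhibition unchanged, and baseline balance would not protect against that. The covariates named in section 8 (age, education and the like) do not address it. Under the carry-forward rule, a zero from a non-responding session would also be carried on if the participant later withdrew.

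**Working it through.** **1. Trial counts.** The go/no-go mix is the only related figure in the plan that can be checked. 46/60 = 76.7%, which rounds to the stated 77%, so there are 46 go and 60 − 46 = 14 no-go stimuli. The stop-signal task has 24 − 6 = 18 go trials.

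**2. The rule applied to individuals.** A participant who presses with probability q whatever the signal has expected errors of 6q and 14q.

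| Participant | Stop-signal errors (of 6) | Go/no-go errors (of 14) | Go trials correct |
|---|---|---|---|
| Never presses (q = 0) | 0 | 0 | 0/18 and 0/46 |
| Indiscriminate, q = 0.5 | 3.0 | 7.0 | 50% |
| Indiscriminate, q = 0.9 | 5.4 | 12.6 | 90% |
| Engaged: 95% go hits, 30% to 50% false presses (assumed) | 1.8 to 3.0 | 4.2 to 7.0 | 95% |

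The non-responder ranks above the engaged participant. A fall in indiscriminate pressing from q = 0.9 to q = 0.5 looks like a gain of 2.4 and 5.6 errors with no change in inhibition. This step needs no assumption about the arms.

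**3. Illustration for the arm comparison.** From the documents: 60 per arm, significance level .05 (taken as two-sided), 6 and 14 inhibition trials. Assumed, because the documents give none of these: failure probability F ~ Beta(4, 6), mean 0.40, the same in both arms; response probability R ~ Beta with mean m and m-dependent parameters summing to 20; errors ~ Binomial(n, F × R).

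- Mean errors = n × 0.40 × m. For m = 0.95: 6 × 0.38 = 2.28 and 14 × 0.38 = 5.32. For m = 0.75: 6 × 0.30 = 1.80 and 14 × 0.30 = 4.20.
- With p = F × R, E(p²) = (0.16 + 0.24/11) × (m² + m(1 − m)/21), and the variance is n[E(p) − E(p²)] + n²[E(p²) − E(p)²].
- Stop-signal, m = 0.95: E(p²) = 0.1645 and variance 2.02. At m = 0.75: E(p²) = 0.1039 and variance 1.68.
- Pooled SD = √((2.02 + 1.68)/2) = 1.36. Standardised difference = 0.48/1.36 = 0.35.
- Chance of p < .05 ≈ Φ(0.353 × √30 − 1.96) = 49%.

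| Response rates | Stop-signal: SD units, chance p < .05 | Go/no-go: SD units, chance p < .05 |
|---|---|---|
| 95% v 75% | 0.35, 49% | 0.45, 69% |
| 95% v 85% | 0.17, 16% | 0.22, 22% |
| 95% v 90% | 0.09, 8% | 0.11, 9% |

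The arm that responds more looks worse. Inhibition is identical in both arms, so each percentage should be 5%. A wider spread of inhibition ability (Beta(1.2, 1.8), same mean) lowers the first row to 0.29 and 0.33 SD, with 36% and 44% significant.

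**4. Scoring both trial types.** Balanced accuracy = (go-hit rate + correct-withhold rate)/2. The non-responder gets (0 + 1)/2 = 0.50, which is chance, and so does every indiscriminate presser. The engaged participant gets (0.95 + 0.70)/2 = 0.825 to (0.95 + 0.50)/2 = 0.725. The ranking is now the right way round.

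**The case against.** The best reply is that a biased comparison needs the arms to differ in key-pressing, and nothing in the documents shows that they would. The engagement attributed to Paro concerns interaction with the robot and with other people, not an individual computer test run by a separate, blinded assistant. Controls also have activities. Severe dementia, severe communication difficulty and total dependence are excluded, and participants practise first. All this stands: it makes gross non-response less likely and leaves the direction of any bias open. It does not alter the scoring rule, under which non-response earns the best score.

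A second reply is that the MMSE and the two working-memory scores are also primary, and on those non-response lowers the score, so wide disengagement would show as a contradictory pattern. That would raise suspicion, but without go-trial data the pattern could not be resolved.

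Two stronger readings about the Stroop task are tempting and are not supported:

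- **That a silent participant also scores well on it.** The plan does not say whether a missing answer is an incorrect response. If it is, a silent participant scores badly.
- **That inability to read biases the arms.** Eligibility asks for communication, not reading, and the MMSE cut-offs include "17/18 for older people without formal education". But that cut-off is taken from a cited prevalence study and does not show who will enrol. Inability to read is also a stable trait that randomisation balances on average. What remains is a less sensitive score: non-readers meet little conflict, and general colour-naming errors are mixed in.

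**Conclusion.** The point holds for the stop-signal and go/no-go tasks. It follows from the stated scoring rules and the trial counts: zero responding gives 0/6 and 0/14, and any arm difference in responding is read as a difference in inhibition. This affects part of a primary outcome and should be changed.

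The size and direction of any effect on the trial result are unknown. The illustrated range, from 0.09 and 0.11 SD (close to the nominal error rate) to 0.35 and 0.45 SD, rests on assumed response rates and an assumed 40% failure rate. A reader might infer that Paro will look harmful because it raises engagement. The documents do not support that: if Paro reduced responding, the same mechanism would produce a false benefit. For the Stroop task the conclusion is reduced sensitivity only.

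**What to change.** In Study 3, section 7(3), for the stop-signal and go/no-go tasks:

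1. Record go-trial hits and score each task on both trial types, for example by balanced accuracy, or by d-prime with a stated correction for rates of 0% or 100%.
2. Report go accuracy by arm and visit beside commission errors. This is needed even with a combined score. With 40% failure, balanced accuracy is 0.5 + 0.95 × 0.6/2 = 0.785 at 95% responding and 0.5 + 0.75 × 0.6/2 = 0.725 at 75%. Non-response is no longer rewarded, but it still moves the score.
3. Pre-set a minimum go-hit rate below which zero commission errors is not read as good inhibition. Report the number of such sessions by arm and add a sensitivity analysis with stated values for them. Do not carry the last value forward: these sessions may be related to arm, and a flagged baseline session has no earlier value.
4. Do not adjust for post-baseline go-hit rate, since treatment may alter it.

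For the Stroop task, score the incongruent minus the congruent error rate, using the 75 congruent trials already given, and state whether a missing answer counts as an error. This removes general colour-naming errors but does not identify non-readers.

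The cost is modest, as no extra testing is needed. The documents say only that the error count is displayed, so whether go-trial responses can be exported must be checked before enrolment. Six stop trials give a coarse index whatever the formula, and some sessions will be flagged as not interpretable.
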